Patients will be approached for participation at their GI clinic visit by the treating clinician and/or physician assistant. After providing informed consent, patients will be randomly assigned to either conventional treatment or genotype-supported PPI therapy using a randomization table. A 5-ml (one teaspoon) venous blood sample will then be drawn by a nurse, physician assistant, or phlebotomist. The patient will be asked to complete 3 surveys/questionnaires: the Reflux Disease Questionnaire (RDQ), Global Overall Symptom (GOS) scale, and a survey to assess knowledge, attitudes, and beliefs about pharmacogenetic testing. Patients will receive a total of \$25 for participating in this study. The \$25 VISA gift card will be provided after completing the final questionnaire. Patients in the control group may be withdrawn prior to completion if they or their physician elect to order the genetic test during the study. These patients would receive a \$10 VISA gift card for their participation up to the point of withdrawal.

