Genotyping and result reporting. Genotyping will be done by the CLIA-licensed UF Pathology Laboratory, as has been done for over 1,600 patients in the UF Health CYP2C19-clopidogrel implementation, with genotype results reported in the EHR. For patients randomized to the genotype-supported arm, genotype results will be available in approximately 2 weeks. For patients randomized to the conventional treatment arm, the genotype results will be resulted in the EHR after the patient completes study participation (12 weeks after patient enrollment). The patient's clinician will be educated about the genotype results and their implication for PPI response. A recommendation for a dose increase will be provided for RMs and UMs (approximately 30% to 35% of patients). For patients with other genotypes, clinicians will be advised that usual PPI doses are expected to be effective that lower doses may be sufficient for symptoms management in PMs. Clinicians will also be provided quick reference guides that will include phenotype, genotype, dosing recommendations, and educational information. The PMP Committee has convened with the GI clinicians to evaluate and approve the dosing recommendations for adults based on CYP2C19 genotype. Clinical decision support tools in the EMR will also be implemented that will provide this guidance to the treating clinician. While dosing recommendations will be provided based on genotype results, the ultimate prescribing decision will be left to the discretion of the treating physician.

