Assessment of PPI efficacy and adverse effects. Our primary outcome will be the effectiveness of PPI therapy, which will be determined via two questionnaires: RDQ and GOS scale, administered by study personnel at baseline and 12 weeks. The RDQ was developed to monitor treatment response over time and evaluates 6 symptoms (12 items) covering 3 domains: heartburn, regurgitation, and upper abdominal pain. Each symptom is evaluated using a 6-point Likert scale to assess frequency and severity over the previous week. Each symptom is rated from 1 (did not have) to 6 (severe), and the RDQ mean score is calculated as the mean response to the 12 items. The RDQ mean score thus ranges from 1 to 6 and has been psychometrically validated. The GOS scale evaluates 18 symptoms, with each rated from 1 (no problem) to 7 (very severe). Similar to the RDQ, the mean score is calculated as the mean response to the 18 items, with mean scores ranging from 1 to 7. Patient participation will end after they complete the approximate 12 week questionnaire. However, we will continue to

follow patients over 24 months through medical record review to assess adverse outcomes for occurrence of upper respiratory infection (cold), sore throat, strep throat, bronchitis, pneumonia, ear infection, acute sinusitis (sinus infection), bone fractures, renal function and gastrointestinal infections.

Metrics for assessing success of pharmacogenetic testing in clinical practice. We will test a variety of variables that will provide insight into attitudes and acceptability of pharmacogenetic testing. These will include: 1) percent of patients approached about the study who agree to participate; 2) surveys of patients and clinic staff on knowledge, attitudes, and beliefs about pharmacogenetic testing; and 3) the percent of the time a dosing recommendation for a patient in the genotype-supported arm is accepted by the clinician. Patients will be surveyed about knowledge, attitudes, and beliefs about pharmacogenetic testing using questionnaires on enrollment and at the end of their study participation. Clinic staff will be surveyed about knowledge, attitudes, and beliefs about testing at the beginning and end of the study.

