With 180 total patients (90 patients in each arm), we expect approximately 30 patients in each arm to have the genotype of interest (i.e. RM or UM). At alpha of 0.05, we will have 80% power to detect effect size of  $\geq 0.74$  in the RDQ score in RMs/UMs. This effect size is equivalent to a RDQ score difference of 1.22 for regurgitation and a score difference of 0.93 for heart burn. These differences in RDQ scores are smaller than what is considered clinically significant. Therefore our study is well-powered.

In summary, by studying a total 180 patients (120 from UF Health and 60 from Nemours), the data suggest we will have excellent power to detect an efficacy endpoint. Data generated from this protocol on adverse effects will also help us define the incidence of the adverse effect phenotypes to inform sample size for a future pragmatic trial examining effects of genotype-supported dosing on PPI safety endpoints.

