Study Design. The study is a randomized, open-label, comparative effectiveness clinical trial in 180 patients (60 children, 120 adults) with GERD or any stomach acid mediated condition that will require a PPI. Patients will volunteer to be randomized to either conventional PPI treatment or genotype-supported PPI treatment. All participants will have symptoms of GERD or related diseases who are candidates for PPI therapy or who are on PPI therapy and classified as refractory GERD. Adult patients will be enrolled at UF Health Gastroenterology Clinics and children will be enrolled at the Nemours Children's Hospital Gastroenterology Clinics. After obtaining informed consent, participants will be genotyped and randomly assigned to either conventional treatment or genotype-supported PPI therapy using a randomization table. At NCH, study participants in the control/conventional arm will be blinded on CYP2C19 metabolizer status. Study staff members will not be blinded to any study procedures or determinations as this will improve and facilitate study feasibility. At the end of study period (i.e. 8-12 weeks) study participants in the control/conventional arm will be revealed of metabolizer phenotype status. We will also collect data from the health records for up to 24 months after enrollment on upper respiratory infection (cold), sore throat, strep throat, bronchitis, pneumonia, ear infection, acute sinusitis (sinus infection), bone fractures, renal function, and gastrointestinal infections for preliminary assessment of the effects of CYP2C19-supported PPI dosing on adverse effects.

Participation stipends. Each participant will receive \$25 dollars at the end of study participation. Participants must have completed all study procedures by the end of the study period in order to receive the complete study stipend. If a study participant decides to withdraw from study before the end of study period (before 3 months), the participant will receive a pro-rated stipend. A deposit will be provided in a single CT Payer master card. Each participant will be provided a CT Payer (master card) at the moment of consent. The CT Payer card will be uploaded with the stipend at the end of study participation. Participants whom insurance coverage is limited, a separate deposit will be provided to cover study therapy expenses. We expect to incur in study drug expenses for participants with higher PPI dose prescriptions than conventional dosing (i.e. RMs and UMs).

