Power calculation. Briefly, with 600 participants in the trial, we will have 80% power at alpha level of 0.05 to detect a relative risk of 1.35 or higher in the GERD control within RM patients in the usual care vs. the genotype-supported arm. This assumes that among the 600 participants, 33% will have the RM phenotype, and half will be randomized to each arm of the study. For the adverse event hypothesis, with 600 patients, we expect to have 178 PM patients, with 89 patients in each arm. At alpha level of 0.05, we will have 80% power to detect relative risk reduction of 29% or more in the adverse events for PM patients in the genotype supported group compared to those in the usual care group.

Clinical Trials.gov. This trial requires registration in ClinicalTrials.gov.

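### The 80% power at an effect size of 0.74 is right for 30 RM/UM patients analysed per arm, but 30 is the number expected to enrol, with no allowance for missing 12-week RDQ scores

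*Combined protocol and SAP*

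**What the plan says.** The sample size for the main hypothesis is in the UF protocol, section 7, Analysis Plan and Power Calculations. It starts from enrolment, "With 180 total patients (90 patients in each arm", and continues: "we expect approximately 30 patients in each arm to have the genotype of interest". The power claim follows: "At alpha of 0.05, we will have 80% power to detect effect size of" 0.74 or more on the RDQ in RMs/UMs. That effect is translated into score differences of 1.22 for regurgitation and 0.93 for heartburn, and from these the section concludes that the study is well powered.

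The one-third share agrees with the rest of the documents. Table 1 gives 28% RM and 5.3% UM, and the Nemours power calculation assumes "33% will have the RM phenotype". The UF section on genotyping and result reporting gives a range: "A recommendation for a dose increase will be provided for RMs and UMs (approximately 30% to 35% of patients".

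The analysis is a linear regression on the RDQ reduction in RM/UM patients, compared between arms. Three provisions bear on who will have a reduction to analyse:

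- UF, Assessment of PPI efficacy and adverse effects: the RDQ and GOS are "administered by study personnel at baseline and 12 weeks".
- UF, Participant Recruitment Methods: "Patients in the control group may be withdrawn prior to completion", where the patient or physician chooses to order the genetic test during the study.
- Nemours, Participation stipends: "If a study participant decides to withdraw from study before the end of study period", the stipend is pro-rated.

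Neither power section mentions loss, and neither protocol says how a missing score is handled.

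**The concern.** A power statement should rest on the number of patients expected in the analysis. Here the number expected to enrol with the relevant genotype goes straight into the formula. A UF patient without the week-12 RDQ has no reduction, and no later or intermediate RDQ can stand in for it. Both protocols foresee some patients leaving early, yet the calculation implies that none will.

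The statement has little slack, so any realistic loss puts power below the stated 80% and raises the detectable difference above 1.22 and 0.93. The well-powered conclusion is drawn from exactly those two differences. A null result could then be read as coming from a trial with 80% power at 0.74 when the analysed sample gave less.

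**Working it through.** **Inputs.** From the UF power section: 90 enrolled per arm, about 30 RM/UM per arm, alpha 0.05, power 80%, effect size d = 0.74, RDQ differences 1.22 and 0.93. From Table 1: RM/UM share 28% + 5.3% = 33.3%. From the UF analysis plan: Student's unpaired t-test for continuous variables. No loss rate is given anywhere, so 5% to 20% is an assumed range.

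**Step 1, where the 30 comes from.** 90 × 0.333 = 29.97 per arm. Nothing is taken off for loss.

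**Step 2, reproduce the stated power.** For a two-sample t-test with n1 and n2 analysed, the noncentrality is d × √(n1·n2/(n1+n2)), with n1 + n2 − 2 degrees of freedom. For 30 v 30 this is 0.74 × √15 = 2.866 on 58 degrees of freedom, with a two-sided critical value of 2.002. Power is 80.5%, and the smallest effect detectable at 80% is 0.736. A normal approximation gives 81.8%. A one-sided test gives 88%, so the stated figure is evidently two-sided. It is correct for 30 analysed per arm.

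**Step 3, equal loss in both arms.** Analysed n per arm = 30 × (1 − loss). The RDQ columns multiply the detectable effect by the SDs that the plan implies: 1.22/0.74 = 1.65 for regurgitation and 0.93/0.74 = 1.26 for heartburn.

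| Assumed loss | n per arm | Power at 0.74 | Effect detectable at 80% | Regurgitation | Heartburn |
|---|---|---|---|---|---|
| As stated in the plan | 30 | 80% | 0.74 | 1.22 | 0.93 |
| 5% | 28.5 | 78.4% | 0.755 | 1.25 | 0.95 |
| 10% | 27 | 76.1% | 0.777 | 1.28 | 0.98 |
| 15% | 25.5 | 73.6% | 0.800 | 1.32 | 1.01 |
| 20% | 24 | 70.9% | 0.826 | 1.36 | 1.04 |

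**Step 4, loss in the control arm only.** This is the pattern that the UF withdrawal rule would produce. 30 v 27 (10% of controls) gives about 78%, and 30 v 24 (20%) about 76%.

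**Step 5, how quickly power goes.** 30 v 29 gives 79.8%, 29 v 29 gives 79.1% and 28 v 28 gives 77.6%. By the normal approximation 29 v 29 is still 80.5%. The decline is gradual.

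**The case against.** The strongest reply is that nothing was miscalculated, and that stands: 80% at 0.74 with 30 per arm is right. What is missing is a planning assumption.

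The input is also openly approximate. A 30% to 35% share means 27 to 31.5 RM/UM per arm, or about 76% to 82% power before any loss. At 35%, a 5% loss still leaves 31.5 × 0.95 = 29.9 per arm. Chance alone gives the RM/UM count a standard deviation of √(180 × 1/3 × 2/3) = 6.3 around 60, about as large as a 10% loss. This is fair as a caution against treating 30 as exact. It does not replace an allowance for loss: genotype frequency varies in both directions, whereas loss only subtracts, and at the low end of the range the two add up.

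The provisions cited are narrower than a general dropout clause. The UF rule covers only control patients for whom the genetic test is ordered. The single follow-up score is a UF feature; Nemours uses weekly questionnaires, although the RDQ is not among the instruments its protocol lists. The Nemours stipend clause therefore bears on RDQ loss only if the children contribute an RDQ. Retention is helped at UF because study personnel administer the RDQ and the full payment follows the final questionnaire. All of this stands, and it means that the rate cannot be inferred from the documents. It does not make zero the natural assumption.

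Two stronger readings are tempting. One is that the stated power is gone as soon as the first patients drop out; Step 5 shows that one patient lost per arm still leaves 79%. The other is to combine attrition with a UF-only RDQ sample of about 20 RM/UM per arm, where power is about 63% before any loss. That fall comes almost entirely from whether Nemours collects the RDQ, which is a separate question and should not be counted as attrition.

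**Conclusion.** The concern holds as an omitted allowance for loss. The stated 80% applies to about 30 RM/UM patients analysed per arm, and the plan supports about 30 enrolled. Under an assumed equal loss of 5% to 20%, the shortfall from 80% is about 2 to 9 percentage points and the detectable effect is about 0.76 to 0.83. Control-only loss of 10% to 20% costs about 2 to 4 points.

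These sizes rest on the assumed loss range, a one-third RM/UM share, a two-sided t-test on complete cases, and RDQ data from all 180 patients. A baseline-adjusted model might recover some precision, but no covariate is specified for the RDQ regression.

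A reader might infer that the well-powered conclusion is overturned. The documents do not support that: they cite a clinically significant RDQ difference without giving its value, so it cannot be shown whether 1.28 or 1.36 exceeds it. What can be said is that the conclusion rests on differences that assume virtually complete follow-up. Nor do the documents, which contain only plans, show what loss occurred.

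**What to change.** In the UF power section:

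1. State an assumed proportion of RM/UM patients without a 12-week RDQ, with a reason for it.
2. Restate power, detectable effect and the two RDQ differences for patients analysed. With 10% as the assumption: 27 per arm, 76% power at 0.74, and 80% power at 0.78, equivalent to 1.28 for regurgitation and 0.98 for heartburn.
3. Qualify the well-powered statement to match, and give the value of the clinically significant difference it is compared with.

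This is a text change. It needs no extra enrolment and no change in procedures; the cost is a somewhat less favourable power statement. For scale only, keeping 30 analysed per arm at 10% loss would take 30/0.9 = 33.3, so 34 RM/UM per arm, or 180/0.9 = 200 enrolled in total.

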### 3. Abstract:

Proton Pump Inhibitors (PPIs) are indicated for the treatment of gastroesophageal reflux disease (GERD), *H. pylori* infection, peptic ulcer disease, and gastric protection in patients at risk for gastrointestinal bleeding. PPIs are among the most commonly prescribed drugs in the world, and their most common indication is GERD. Refractory GERD is the term used to describe non-responsiveness to conventional PPI therapy, and it occurs in up to 40% of patients even when the PPI dose is doubled. The efficacy of PPIs is highly dependent on plasma concentrations achieved following drug administration. All PPIs are metabolized in part by the *CYP2C19* enzyme, which is encoded by the highly polymorphic *CYP2C19* gene. Depending on the *CYP2C19* genotype, individuals are classified into different metabolizer phenotypes: poor metabolizers (PM, 2 loss-of-function *CYP2C19* alleles); intermediate metabolizers (IM, one loss-of-function allele); normal metabolizers (NM, no loss or gain-of-function alleles); rapid metabolizer (RM; one gain-of-function allele) and ultra-rapid metabolizers (UM, two gain-of function-alleles). Genetic variants in *CYP2C19* are known to profoundly influence PPI plasma concentrations and consequently, response to PPI therapy. For example, individuals classified as either RM or UM have lower PPI concentrations compared to NM, IMs, or PMs, respond poorly to PPI therapy, and some fail to respond even when the PPI dose is increased. **We hypothesize that genotype-supported treatment of GERD and dyspepsia will lead to better GERD control and improvement in severity of dyspepsia symptoms compared to conventional treatment.** We will conduct a comparative effectiveness study of genotype-supported vs. conventional treatment of GERD and dyspepsia. Patients presenting with GERD or dyspepsia symptoms and either 1) being initiated on PPI therapy or 2) with continued symptoms on current PPI therapy will be recruited from gastroenterology clinics and randomized to a genotype-supported versus conventional PPI therapy management strategy. We will integrate individual *CYP2C19* genotype information into treatment decisions for the genotype-supported arm and compare change in symptom control from baseline to the end of the study between study arms. Given that PPI efficacy is related to PPI exposure and to metabolizer phenotype, individualizing treatment using *CYP2C19* genotype information is expected to improve symptom

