linked PPI use with the risk of chronic kidney disease (CKD) and with progression to end-stage renal failure (ESRD). Additionally, there is evidence suggesting that higher daily PPI doses and/or the degree of acid suppression increase risk for PPI-associated adverse effects, thereby supporting a role for *CYP2C19* genetic variation contributing to adverse events. While the primary focus of this proposal is the impact of *CYP2C19* genotype-supported management of GERD and dyspepsia, we will also collect follow-up data on the occurrence of gastrointestinal and pulmonary/upper respiratory infections, bone fracture, and adverse kidney outcomes to begin building evidence on whether genotype-supported treatment of GERD and dyspepsia may influence risk for adverse outcomes.

This study is significant because it will prospectively test the hypothesis that genotype-supported treatment in patients with GERD and/or dyspepsia leads to better symptom control compared to conventional treatment. Data on adverse events with *CYP2C19*-supported treatment gained from this study will be used to inform power calculations for a larger study focused on preventing PPI-associated adverse events through genotype-supported dosing.

Table 2. Comparison of lansoprazole plasma concentrations by *CYP2C19* phenotype.

Phenotype	Alleles	Number Participants	Mean $\pm$ LZ Con. ng/ml
NM	*1/*1	11	199 $\pm$ 137
IM	*1/*2 or *3	13	303 $\pm$ 165
RM	*1/*17	11	168 $\pm$ 146
UM	*17/*17	2	156 $\pm$ 123
?	*2/*17	4	201 $\pm$ 57.1

A companion study in children will be conducted at Nemours Children's Hospital Gastroenterology Clinics in Orlando. The preliminary data below were generated by investigators at Nemours and helped to inform sample size calculations for our study.

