### **Analysis Plan and Power Calculations:**

We will test the hypothesis that RMs/UMs (1 or 2 gain-of-function alleles) in the genotype-supported arm have better GERD and symptom control than RMs/UMs in the conventional treatment group because they will have their dose increased based on their genotype.

Continuous variables will be compared between the genotype-supported group and the conventional treatment group using the Student's unpaired *t*-test, and categorical variables will be compared using the chi-square or Fisher's exact test. The hypotheses will be tested using linear regression analysis to estimate the difference in the RDQ reduction in the RM/UM patients between the two arms. All analysis will be performed in SAS 9.4 (Cary, NC).

We will evaluate the percentage of the time when a dosing recommendation was made and accepted by the treating clinician, to provide practical data on the willingness of clinicians to adopt this approach. We will also collect patient- and provider-level survey data on knowledge, attitudes, and beliefs about pharmacogenetics testing, using survey tools adapted from other IRB-approved studies.

Power calculation. While there are no data in the literature on genotype associations with the efficacy endpoint we will use (symptom improvement), there are pH probe data by genotype that were generated by the Nemours investigators, that we can use, and this should be an excellent surrogate for symptom data. We have done power calculations based on two of the pH-based response phenotypes, found in Table 3. Specifically we powered based on percent time with pH < 4 (which has an effect size of 0.79) and acid clearance time (effect size of

0.45). Based on these two phenotypes, we have the following power to detect differences in efficacy between *CYP2C19\*17* carriers and non-carriers:

Based on the previous data for acid clearance time, with 180 total participants (120 from UF Health and 60 from Nemours), we have 81% power to detect a 0.49 effect size.

Based on the previous data for time with pH <4.0, with 180 participants, we have >99% power to detect a 0.79 effect size.

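### The efficacy hypothesis is stated for all GERD/dyspepsia patients, but the planned test and its 80% power cover only the RM/UM third, so the claim of excellent power for 180 patients is not supported for the hypothesis as stated

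*Combined protocol and SAP*

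**What the plan says.** The adult protocol gives its efficacy hypothesis in two forms.

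- **Unrestricted.** The Background says of the study that "it will prospectively test the hypothesis that genotype-supported treatment in patients with GERD and/or dyspepsia leads to better symptom control compared to conventional treatment". The Abstract and section 6 (Specific Aim) set genotype-supported against conventional treatment in the same way, with no limit by phenotype. The Abstract also undertakes to "compare change in symptom control from baseline to the end of the study between study arms".
- **RM/UM only.** In section 7, Analysis Plan and Power Calculations opens by naming RMs/UMs in one arm against RMs/UMs in the other as the hypothesis to be tested. The reason given is that these patients will have had their dose raised. A linear regression of RDQ reduction in RM/UM patients is assigned to it. The same part carries a general line: "Continuous variables will be compared between the genotype-supported group and the conventional treatment group using the Student's unpaired" t-test. That line names no outcome.

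On power: "With 180 total patients (90 patients in each arm), we expect approximately 30 patients in each arm to have the genotype of interest". Then: "At alpha of 0.05, we will have 80% power to detect effect size of" 0.74 or more on the RDQ in RMs/UMs. Two other figures, 81% and above 99%, compare carriers of the gain-of-function allele with non-carriers and rest on pH-probe data. The section calls the study well powered and closes, for 180 patients, with "the data suggest we will have excellent power to detect an efficacy endpoint". The opening of section 7 likewise describes 180 patients as enough for the efficacy endpoint and points to the power calculation.

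On treatment advice (Genotyping and result reporting): "A recommendation for a dose increase will be provided for RMs and UMs (approximately 30% to 35% of patients". For other genotypes the clinician is told that usual doses should work, and that less may suffice in PMs.

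**The concern.** Anyone who reads the Abstract, Background or Aim will take the trial's question to be whether genotype-supported treatment helps patients with GERD or dyspepsia in general, and will look for the arm-against-arm result. The plan gives no power for that result, but tells the reader that 180 patients provide excellent power.

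By the plan's own reasoning, the benefit comes from raising the dose in about a third of patients. An effect confined to that third is diluted about threefold when whole arms are compared. A non-significant arm-wide difference could then be read as evidence against genotype-supported treatment, when the trial had little chance of showing one. Two differing hypotheses also leave room to choose the headline comparison after the data are seen.

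**Working it through.** **Inputs.** From the power calculation: alpha 0.05 (taken as two-sided), effect size 0.74 in RM/UM, 90 patients per arm, about 30 RM/UM per arm. From Genotyping and result reporting: RM/UM share 30% to 35%. Table 1 gives 28% + 5.3% = 33.3%. The documents give no effect size for other patients and no dropout rate; none is applied.

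**Method.** Two-sample t-test with n per arm and standardised difference d. Noncentrality = d × √(n/2), with 2n − 2 degrees of freedom. A hand check is power ≈ Φ(noncentrality − 1.96).

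**1. The plan's own figure.** n = 30, d = 0.74: noncentrality 0.74 × √15 = 2.87. Power is 80.5% by t-test and 81.8% by the normal check. The stated 80% is reproduced. A one-sided test would give 88.9%, so two-sided is the matching reading.

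**2. Arm-wide comparison, benefit confined to RM/UM (assumption).** Average difference = 0.74 × share. At one third this is 0.247 SD, and with n = 90 the noncentrality is 0.247 × √45 = 1.65.

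| RM/UM share | Average effect (SD) | Power, 90 per arm |
|---|---|---|
| 30% | 0.222 | 31.6% |
| 33.3% | 0.247 | 37.7% |
| 35% | 0.259 | 40.8% |

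The normal check at one third gives 38.0%. Letting the SD include the extra variance from mixing responders and non-responders gives 36.2%. For 80% power at 0.247 SD, about 259 per arm would be needed.

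**3. Arm-wide comparison, some effect g in the other two thirds.** Average difference = 0.74/3 + 2g/3.

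| g (SD) | Average effect (SD) | Power, 90 per arm |
|---|---|---|
| 0 | 0.247 | 37.7% |
| 0.1 | 0.313 | 55.2% |
| 0.2 | 0.380 | 71.7% |
| 0.3 | 0.447 | 84.6% |

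The average effect detectable with 80% power at 90 per arm is 0.420 SD. This is reached at g = (0.420 − 0.247) × 1.5 = 0.26 SD.

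**4. If only the adults supply RDQ data.** The 180 comprise 120 adults and 60 children. The outcome questionnaires listed for the children's site (Assessment of PPI adverse events and efficacy, in the Nemours part) are the GASP-Q, SN-5, PedsQL gastrointestinal module and a safety questionnaire. The RDQ is not among them. With 120 adults there are 60 per arm and about 60/3 = 20 RM/UM per arm. RM/UM test at 0.74 SD: 62.6%. Arm-wide test at 0.247 SD: 26.8%.

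**The case against.** The strongest reply is that the powered test is the planned test. The Analysis Plan states the RM/UM hypothesis in its first sentence and gives it a matching regression, and the 80% is said outright to be for RMs/UMs. The children's plan frames its efficacy hypothesis by rapid-metabolizer status too. The general t-test line names no outcome and is not called a hypothesis test. The sufficiency remark in section 7 sends the reader to the calculation. All of that stands. It places the fault in the mismatch between the Abstract, Background and Aim on one side and the Analysis Plan on the other, and in the summary wording on power.

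A reader might go further and infer that the trial simply has 38% power. The documents do not support that. The figure needs an effect of exactly zero in two thirds of patients, which they never state, and a true RM/UM effect of 0.74, which the plan gives as detectable rather than expected. The usual-dose advice makes a near-zero effect elsewhere plausible in adults. For children, however, the Nemours dosing section also recommends changed doses for PMs and IMs. At Table 1 frequencies that is (20% + 1.7%) × 60, about 13 children, and the documents give no size or direction for the resulting effect on symptoms.

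A reader might also infer an arithmetic error in the 80%. There is none.

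**Conclusion.** The concern holds as a point of internal consistency. The Abstract, Background and Specific Aim state a hypothesis for all patients. The hypothesis test and the only between-arm power figure belong to RM/UM patients. The carrier-versus-non-carrier figures do not concern the randomised comparison, so they cannot fill the gap. The statements that 180 patients give sufficient or excellent power are therefore unsupported for the unrestricted hypothesis.

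The size of the gap is conditional: about 38% arm-wide power if the benefit is 0.74 SD in RM/UM and zero elsewhere, and at least 80% only if other patients gain about 0.26 SD or more. These figures assume a two-sided 0.05 level, equal SDs, no dropout and RDQ scores on all 180 patients. The last assumption is open to doubt on the children's questionnaire list. Without it, the RM/UM power falls to about 63% and the fully diluted arm-wide power to about 27%.

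**What to change.** - In the Abstract, Background and Specific Aim, state the efficacy hypothesis for RM/UM patients, as the Analysis Plan does.
- In the opening of section 7 and in the power calculation, limit the power statement to the RM/UM comparison and remove the claim of excellent power for the 180-patient trial.
- Label the arm-wide RDQ difference as a secondary estimate, reported with a confidence interval and not used to accept or reject the hypothesis. If a power is quoted for it, give it as conditional: about 38% (32% to 41% over the stated share) with no effect outside RM/UM, and about 55%, 72% and 85% at 0.1, 0.2 and 0.3 SD.
- State that the power figures assume RDQ data on all 180 patients, and give the adult-only values (about 63% for RM/UM, about 27% arm-wide) beside them.

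This changes wording only. No extra patients are needed for it. The price is a narrower stated hypothesis and a less favourable power statement.
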